APPENDIX 2. qFAF FINDINGS

Increase in quantitative auto fluorescence in central macula – The Delori grid is placed on the qFAF image with its edge just touching the optic nerve head. There are 29 zones within the grid and average qFAF units in the 4 rings are calculated after blood vessels are masked. A 12% increase in qFAF units in the mid ring (8 zones) would exceed test-retest variability and will be considered a change from baseline.

Area of abnormal auto fluorescence– quantitative assessment of any abnormal patterns of auto fluorescence in the macular region that may be indicative of disease of the RPE ([Donnalpally 2017](#)). The pattern of auto-fluorescence will be reported as normal or abnormal.

Decrease in auto fluorescence in central macula – qualitative assessment of decreased intensity of auto fluorescence noted within the central 6000 μm diameter is indicative of decreased function of RPE, masking or even RPE atrophy. This will be reported as Yes/No to presence of hyper-auto fluorescence or hypo-auto fluorescence.

Geographic atrophy of the RPE – quantitative measure of areas of missing RPE; no production of auto fluorescence (area of the region of hypo-auto fluorescence), representing region of RPE death (in square millimeters).

APPENDIX 3. ESTIMATE OF TOTAL BLOOD VOLUME COLLECTED DURING THE STUDY PERIOD

Note:

Total blood sampling volume for the individual participants participating in the study is approximately 135 mL.

The actual times of blood sampling may change. Additional blood samples may be taken for safety assessments as required by the PI or at times specified by the sponsor, provided the total volume taken during the study does not exceed 140 mL during the study including planned blood draws.

Procedure	Sample	Volume per sample (mL)	No. samples per participant	Total volume per participant (mL)
Laboratory test	G6PD testing	Blood volume for this sample will come from 4 mL hematology tube at screening		
	CBC	4	8	32
	MetHb%	4	7	28
	Biochemistry	5	7	35
	Serology	5	1	5
	Endocrinology (pregnancy)	5	2	10
Pharmacokinetic test	PK analysis	5	5	25
			TOTAL	135

APPENDIX 4. CENTRAL FOVEAL THICKNESS (CENTRAL 1 MM CIRCLE) ON SPECTRALIS DEVICE

Normative interval based on a literature review of the following publications: Mean = 260 to 280 μm : take 270 μm (across different races) SD ranges from 16 to 24: take 24 μm (the largest study has this SD) Mean \pm 2 SD = 222 to 318 μm (cover male and female range) using 24 μm as the SD	
Citation	CFT Finding
Grover 2009	20-40 years old: 275 \pm 24 (N = 19) 41-60 years old: 269 \pm 22 (N = 20) 61+ years old: 263 \pm 20 (N = 11)
Wenner 2011	N = 34 adults aged 19-30 years old. 29 scan pattern: 281 \pm 17 49 scan pattern: 281 \pm 17 97 scan pattern: 281 \pm 17
Choovuthayakorn 2012	N = 368 adults aged 49 \pm 17 years old. Whole group: 259 \pm 19 Male: 265 \pm 19 Female: 252 \pm 18
Appukuttan 2014	N = 105 adults aged 20-75 years' old Whole group: 260 \pm 19 Male: 266 \pm 19 Female: 255 \pm 16

APPENDIX 5. LEEDS SLEEP EVALUATION QUESTIONNAIRE**How would you describe the way you currently fall asleep in comparison to usual?**

- | | | | |
|----|----------------------------------|-------|----------------------------|
| 1. | More difficult
than usual | _____ | Easier than
usual |
| 2. | Slower than
usual | _____ | More quickly
than usual |
| 3. | I feel less sleepy
than usual | _____ | More sleepy
than usual |

How would you describe the quality of your sleep compared to normal sleep?

- | | | | |
|----|--|-------|--|
| 4. | More restless
than usual | _____ | Calmer than
usual |
| 5. | With more
wakeful periods
than usual | _____ | With less
wakeful periods
than usual |

How would you describe your awakening in comparison to usual?

- | | | | |
|----|--|-------|-----------------------|
| 6. | More difficult
than usual | _____ | Easier than
usual |
| 7. | Requires a
period of time
longer than
usual | _____ | Shorter than
usual |

How do you feel when you wake up?

- | | | | |
|----|-------|-------|-------|
| 8. | Tired | _____ | Alert |
|----|-------|-------|-------|

How do you feel now?

- | | | | |
|----|-------|-------|-------|
| 9. | Tired | _____ | Alert |
|----|-------|-------|-------|

How would you describe your balance and co-ordination upon awakening?

- | | | | |
|-----|------------------------------|-------|------------------------------|
| 10. | More disrupted
than usual | _____ | Less disrupted
than usual |
|-----|------------------------------|-------|------------------------------|

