9.2.8. Leeds Sleep Evaluation Questionnaire (LSEQ)

The LSEQ is a participant assessment of the difficulty of falling asleep, quality of sleep, awakening from sleep, and behavior following wakefulness as these factors can be causative or related to psychiatric disorders ([Zisapel 2003](#)). This questionnaire was developed as a clinical investigation tool to retrospectively measure sleep patterns prior to study participation.

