Change from baseline in BCVA, key SD-OCT continuous parameters, and LSEQ component scores will be analyzed by a random intercept mixed model to account for correlation between repeated measures. Treatment effect (difference and 95% CI) on the change from baseline variables will be estimated across study visits.

Specifically, the following assessments will be conducted for secondary safety endpoints, and the extra analyses, if mentioned as below, will be applied.

- Mean change from baseline in key SD-OCT parameters including CST, TMV volume, and parafoveal (inner ring of ETDRS grid) retinal thickness and the proportion of participants with ellipsoid or interdigitating zone disruption. The difference in the proportion of participants with clinically significant ophthalmologic changes (as defined in the primary endpoint) between treatment group and the placebo group will be calculated. In addition, the change from baseline in individual SD-OCT and qFAF parameters listed in [Appendix 1](#) and [Appendix 2](#) will be tabulated and compared between tafenoquine and placebo-treated groups.
- Proportion of participants with abnormal changes from baseline observed on qFAF using the Spectralis HRA+OCT device with grey scale values extracted from these images for statistical analysis using qFAF software (Heidelberg Engineering).
- Mean change from baseline in BCVA. Changes from baseline in BCVA results by the ETDRS chart will be tabulated and compared between the two groups. A clinically significant deterioration is defined as a reduction of more than 4 letters from baseline (Week 1, Day 1 [Visit 2]) of 0.08 logMAR. The M-chart will be used to quantify the severity of the distortion (if detected). An additional analysis of BCVA changes will include the proportion of participants experiencing a 1-4 letter change (less than one line of ETDRS visual acuity change), a 5-9 letter change (1 line, but less than 2-line change), 10-14 letter change (2 lines, less than 3 lines) or 15 or more letter change (3 lines or more) in BCVA from baseline. A ≥ 15 letter (≥ 3 line) or more change in ETDRS BCVA at 4 meters is considered clinically significant.

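### LSEQ: eight of ten items are already ratings against an undefined 'usual', so analysing change from Day 1 without stated baseline adjustment is inefficient, and lasting worsening may be understated at later visits

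*Combined protocol and SAP*

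**What the plan says.** Appendix 5 reproduces the questionnaire. Items 1-3 come under "How would you describe the way you currently fall asleep in comparison to usual", items 4-5 under "How would you describe the quality of your sleep compared to normal sleep" and items 6-7 under "How would you describe your awakening in comparison to usual". Item 10 is headed "How would you describe your balance and co-ordination upon awakening". The response lines of all eight run between ends worded relative to usual. Only item 8 ("How do you feel when you wake up") and item 9 ("How do you feel now") are absolute, from tired to alert.

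The schedule in Section 1 gives the LSEQ at Day 1 and Weeks 4, 12, 24, 52 and 64. Section 8.2 places the Day 1 administration before randomisation, and Section 9.1 makes the pre-dose Day 1 assessment the baseline. The endpoint in Section 5.2.2 is the mean change from baseline in four component scores (GTS, QOS, AFS, BFW). On the analysis, Section 12.2.3.2 says: "Change from baseline in BCVA, key SD-OCT continuous parameters, and LSEQ component scores will be analyzed by a random intercept mixed model". It adds that the treatment effect will be estimated across visits. It does not mention the Day 1 score as a covariate.

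Section 9.2.8 describes the tool thus: "This questionnaire was developed as a clinical investigation tool to retrospectively measure sleep patterns prior to study participation". No section gives participants a definition of usual, a recall window or an item-to-component scoring rule.

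**The concern.** There are two separate issues.

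**Efficiency.** A post-dose answer to items 1-7 or 10 is already a comparison with the participant's own reference. Subtracting a Day 1 answer to the same question gives a change of a change. Unless the two answers are strongly correlated, the subtraction mostly adds the noise of the Day 1 rating.

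**Reference period.** Usual is not fixed in time. A participant whose sleep worsened early and stayed worse could truthfully answer at Week 52 that sleep is as usual. In an affected arm this would pull scores towards no difference, and the placebo arm would not correct it, because participants whose sleep has not changed have nothing to re-anchor to.

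Section 3 names sleep disturbance assessed by the LSEQ as something the trial will characterise, and the purpose of the trial is exposure beyond six months. The later visits are therefore the ones that matter most, and an error towards no difference is the reassuring direction in a safety study.

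**Working it through.** The documents give no LSEQ effect size, standard deviation, correlation or power, so there is no planned figure to reproduce. Both calculations below rest on assumptions.

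**1. Cost of the subtraction.** Let each score have variance s² at Day 1 and at a given post-dose visit (equal variances assumed), with correlation rho between them.

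- Raw post-dose score: s².
- Change from Day 1: 2s²(1 - rho).
- Post-dose score adjusted for Day 1: s²(1 - rho²).
- Adjusted over change: (1 - rho²) / [2(1 - rho)] = (1 + rho)/2.

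| rho (assumed) | change / raw = 2(1-rho) | adjusted / change = (1+rho)/2 |
|---|---|---|
| 0 | 2.0 | 0.50 |
| 0.3 | 1.4 | 0.65 |
| 0.5 | 1.0 | 0.75 |

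These ratios are per visit. Without equal variances (s0² at Day 1, s1² post-dose), the change-score variance equals the adjusted variance plus (s0 - rho·s1)². That extra term is never negative, so adjustment is never worse, apart from the small cost of estimating one slope.

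**2. Does the subtraction cause bias?** Day 1 is collected before randomisation, so its expected value is the same in both arms. The expected between-arm difference in change therefore equals the expected difference in post-dose scores. Any shrinkage from a moving reference is present in both analyses.

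**3. Size of the reference-period risk (illustration only).** Assume a constant true worsening of 10 units on a usual-anchored item through Week 52, gone at Week 64. Assume also that usual drifts towards current sleep with half-life h weeks. The on-treatment score at week t is then -10 × 2^(-t/h). At Week 64 the score is +10 × (1 - 2^(-52/h)) × 2^(-12/h).

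| h (assumed) | Wk 4 | Wk 12 | Wk 24 | Wk 52 | Wk 64 | Mean, Wks 4-64 |
|---|---|---|---|---|---|---|
| 4 | -5.0 | -1.3 | -0.2 | 0.0 | +1.2 | -1.0 |
| 12 | -7.9 | -5.0 | -2.5 | -0.5 | +4.8 | -2.2 |
| 26 | -9.0 | -7.3 | -5.3 | -2.5 | +5.4 | -3.7 |
| 52 | -9.5 | -8.5 | -7.3 | -5.0 | +4.3 | -5.2 |
| no drift | -10 | -10 | -10 | -10 | 0 | -8.0 |

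The mean weights the five visits equally. Recovery after stopping could score as improvement at Week 64.

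**4. Absolute items.** Items 8 and 9 do not re-anchor in this way. If they form a three-item component with item 10, which the order of the headings suggests but no section states, the Week 52 score is [2 × (-10) - 10 × 2^(-52/h)]/3. That gives -6.7, -6.8 and -7.5 for h = 4, 12 and 26.

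**The case against.** A reader might infer that lasting worsening will become the new usual and score as no change. The documents do not support that. Complete loss needs every affected participant to re-anchor fully, and nothing in the text shows this happening or how fast. Section 9.2.8 is the only statement of a reference period and can be read as pointing to pre-study sleep, although that never reaches the participant in the item wording. Week 4 would catch part of an early effect at any of the rates above, and items 8-9 would still respond.

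A reader might also blame the change-from-baseline rule for the understatement. Step 2 shows that this is wrong. Adjusting for Day 1 improves precision but does nothing about a moving reference.

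The efficiency loss is conditional too. Section 12 defers detail to a further statistical analysis plan. If that plan fits Day 1 as a covariate, modelling change and modelling the post-dose score give the same treatment estimate and interval, and the loss disappears. The current text does not say so.

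Finally, the LSEQ is one of many secondary endpoints, and sleep complaints are also collected as adverse events at each visit, so sleep worsening is not otherwise unobserved. A wording change during the study has real costs: Appendix 8 shows that recruitment began well before the current version, so participants could answer two forms of the questionnaire, and the mix could differ between the Australian and the later US sites.

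All of these points stand. They limit the concern but leave the unadjusted comparison and the unreconciled reference period in place.

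**Conclusion.** The point holds in limited form.

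- **Textual.** Eight of ten items are rated against a usual that no section ties to pre-dose sleep, while Section 12.2.3.2 analyses their change from Day 1 with no stated baseline adjustment.
- **Efficiency.** Adjusting for Day 1 would give 0.50 to 0.75 of the change-score variance per visit for rho between 0 and 0.5. This assumes equal variances and a correlation that the documents do not give.
- **Understatement.** This is a risk and not an established bias. Under the assumed half-lives of 12 to 52 weeks, the mean over Weeks 4-64 falls from -8.0 to between -2.2 and -5.2. Those figures illustrate how far the result depends on the assumed rate and do not estimate what will happen. The source is the item wording, and items 8-9 and adverse event reports offset part of it.

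**What to change.** 1. In Section 12.2.3.2, compare the post-dose LSEQ component scores between arms by visit, with the Day 1 score as a covariate. This uses data already collected and needs only analysis-plan wording before unblinding.
2. As a sensitivity display, show the absolute items (8-9) separately from the comparative items (1-7 and 10). State the item-to-component scoring, which the documents do not give. This costs one additional table.
3. Reconcile Section 9.2.8 with Appendix 5 on the reference period.
4. If an instruction is added that usual means before the first study tablet, flag records collected before and after it and report that flag by arm and site. Note that participants at Week 52 or 64 would be recalling sleep from a year or more earlier. This step is the only one that addresses the moving reference, and the only one with a material cost: two versions of the questionnaire and imperfect recall. If it is not taken, the report should say that later-visit LSEQ results may understate sustained worsening.

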APPENDIX 6. DIZZINESS HANDICAP INVENTORY

P1. Does looking up increase your problem?	 Yes  Sometimes  No
E2. Because of your problem, do you feel frustrated?	 Yes  Sometimes  No
F3. Because of your problem, do you restrict your travel for business or recreation?	 Yes  Sometimes  No
P4. Does walking down the aisle of a supermarket increase your problems?	 Yes  Sometimes  No
F5. Because of your problem, do you have difficulty getting into or out of bed?	 Yes  Sometimes  No
F6. Does your problem significantly restrict your participation in social activities, such as going out to dinner, going to the movies, dancing, or going to parties?	 Yes  Sometimes  No
F7. Because of your problem, do you have difficulty reading?	 Yes  Sometimes  No
P8. Does performing more ambitious activities such as sports, dancing, household chores (sweeping or putting dishes away) increase your problems?	 Yes  Sometimes  No
E9. Because of your problem, are you afraid to leave your home without having someone accompany you?	 Yes  Sometimes  No
E10. Because of your problem have you been embarrassed in front of others?	 Yes  Sometimes  No
P11. Do quick movements of your head increase your problem?	 Yes  Sometimes  No
F12. Because of your problem, do you avoid heights?	 Yes  Sometimes  No
P13. Does turning over in bed increase your problem?	 Yes  Sometimes  No
F14. Because of your problem, is it difficult for you to do strenuous homework or yard work?	 Yes  Sometimes  No
E15. Because of your problem, are you afraid people may think you are intoxicated?	 Yes  Sometimes  No
F16. Because of your problem, is it difficult for you to go for a walk by yourself?	 Yes  Sometimes  No
P17. Does walking down a sidewalk increase your problem?	 Yes  Sometimes  No
E18. Because of your problem, is it difficult for you to concentrate	 Yes  Sometimes  No
F19. Because of your problem, is it difficult for you to walk around your house in the dark?	 Yes  Sometimes  No

DIZZINESS HANDICAP INVENTORY (CONT)

E20. Because of your problem, are you afraid to stay home alone?	 Yes  Sometimes  No
E21. Because of your problem, do you feel handicapped?	 Yes  Sometimes  No
E22. Has the problem placed stress on your relationships with members of your family or friends?	 Yes  Sometimes  No
E23. Because of your problem, are you depressed?	 Yes  Sometimes  No
E24. Does your problem interfere with your job or household responsibilities?	 Yes  Sometimes  No
E25. Does bending over increase your problem?	 Yes  Sometimes  No

APPENDIX 7: COLUMBIA-SUICIDE SEVERITY RATING SCALE

SUICIDAL IDEATION	
Ask questions 1 and 2. If both are negative, proceed to "Suicidal Behavior" section. If the answer to question 2 is "yes", ask questions 3, 4 and 5. If the answer to question 1 and/or 2 is "yes", complete "Intensity of Ideation" section below.	Since Last Visit
1. Wish to be Dead Subject endorses thoughts about a wish to be dead or not alive anymore, or wish to fall asleep and not wake up. Have you wished you were dead or wished you could go to sleep and not wake up? If yes, describe:	Yes No  
2. Non-Specific Active Suicidal Thoughts General, non-specific thoughts of wanting to end one's life/commit suicide (e.g., "I've thought about killing myself") without thoughts of ways to kill oneself/associated methods, intent, or plan during the assessment period. Have you actually had any thoughts of killing yourself? If yes, describe:	Yes No  
3. Active Suicidal Ideation with Any Methods (Not Plan) without Intent to Act Subject endorses thoughts of suicide and has thought of at least one method during the assessment period. This is different than a specific plan with time, place or method details worked out (e.g., thought of method to kill self but not a specific plan). Includes person who would say, "I thought about taking an overdose but I never made a specific plan as to when, where or how I would actually do it...and I would never go through with it." Have you been thinking about how you might do this? If yes, describe:	Yes No  
4. Active Suicidal Ideation with Some Intent to Act, without Specific Plan Active suicidal thoughts of killing oneself and subject reports having some intent to act on such thoughts , as opposed to "I have the thoughts but I definitely will not do anything about them." Have you had these thoughts and had some intention of acting on them? If yes, describe:	Yes No  
5. Active Suicidal Ideation with Specific Plan and Intent Thoughts of killing oneself with details of plan fully or partially worked out and subject has some intent to carry it out. Have you started to work out or worked out the details of how to kill yourself? Do you intend to carry out this plan? If yes, describe:	Yes No  
INTENSITY OF IDEATION	
The following features should be rated with respect to the most severe type of ideation (i.e., 1-5 from above, with 1 being the least severe and 5 being the most severe). Most Severe Ideation: _____ 
 Type # (1-5) Description of Ideation 
	Most Severe
Frequency How many times have you had these thoughts? (1) Less than once a week (2) Once a week (3) 2-5 times in week (4) Daily or almost daily (5) Many times each day	_____
Duration When you have the thoughts, how long do they last? (1) Fleeting - few seconds or minutes (4) 4-8 hours/most of day (2) Less than 1 hour/some of the time (5) More than 8 hours/persistent or continuous (3) 1-4 hours/a lot of time	_____
Controllability Could/can you stop thinking about killing yourself or wanting to die if you want to? (1) Easily able to control thoughts (4) Can control thoughts with a lot of difficulty (2) Can control thoughts with little difficulty (5) Unable to control thoughts (3) Can control thoughts with some difficulty (6) Does not attempt to control thoughts	_____
Deterrents Are there things - anyone or anything (e.g., family, religion, pain of death) - that stopped you from wanting to die or acting on thoughts of committing suicide? (1) Deterrents definitely stopped you from attempting suicide (4) Deterrents most likely did not stop you (2) Deterrents probably stopped you (5) Deterrents definitely did not stop you (3) Uncertain that deterrents stopped you (6) Does not apply	_____
Reasons for Ideation What sort of reasons did you have for thinking about wanting to die or killing yourself? Was it to end the pain or stop the way you were feeling (in other words you couldn't go on living with this pain or how you were feeling) or was it to get attention, revenge or a reaction from others? Or both? (1) Completely to get attention, revenge or a reaction from others (4) Mostly to end or stop the pain (you couldn't go on living with the pain or how you were feeling) (2) Mostly to get attention, revenge or a reaction from others (5) Completely to end or stop the pain (you couldn't go on living with the pain or how you were feeling) (3) Equally to get attention, revenge or a reaction from others and to end/stop the pain (6) Does not apply	_____

SUICIDAL BEHAVIOR (Check all that apply, so long as these are separate events; must ask about all types)		Since Last Visit
Actual Attempt: A potentially self-injurious act committed with at least some wish to die, as a result of act. Behavior was in part thought of as method to kill oneself. Intent does not have to be 100%. If there is any intent/desire to die associated with the act, then it can be considered an actual suicide attempt. There does not have to be any injury or harm , just the potential for injury or harm. If person pulls trigger while gun is in mouth but gun is broken so no injury results, this is considered an attempt. Inferring Intent: Even if an individual denies intent/wish to die, it may be inferred clinically from the behavior or circumstances. For example, a highly lethal act that is clearly not an accident so no other intent but suicide can be inferred (e.g., gunshot to head, jumping from window of a high floor/story). Also, if someone denies intent to die, but they thought that what they did could be lethal, intent may be inferred. Have you made a suicide attempt? Have you done anything to harm yourself? Have you done anything dangerous where you could have died? What did you do? Did you _____ as a way to end your life? Did you want to die (even a little) when you _____? Were you trying to end your life when you _____? Or did you think it was possible you could have died from _____? Or did you do it purely for other reasons / without ANY intention of killing yourself (like to relieve stress, feel better, get sympathy, or get something else to happen)? (Self-Injurious Behavior without suicidal intent) If yes, describe:	Yes No   Total # of Attempts _____ Yes No  	
Has subject engaged in Non-Suicidal Self-Injurious Behavior? Interrupted Attempt: When the person is interrupted (by an outside circumstance) from starting the potentially self-injurious act (if not for that, actual attempt would have occurred). Overdose: Person has pills in hand but is stopped from ingesting. Once they ingest any pills, this becomes an attempt rather than an interrupted attempt. Shooting: Person has gun pointed toward self, gun is taken away by someone else, or is somehow prevented from pulling trigger. Once they pull the trigger, even if the gun fails to fire, it is an attempt. Jumping: Person is poised to jump, is grabbed and taken down from ledge. Hanging: Person has noose around neck but has not yet started to hang - is stopped from doing so. Has there been a time when you started to do something to end your life but someone or something stopped you before you actually did anything? If yes, describe:	Yes No   Total # of interrupted _____	
Aborted Attempt: When person begins to take steps toward making a suicide attempt, but stops themselves before they actually have engaged in any self-destructive behavior. Examples are similar to interrupted attempts, except that the individual stops him/herself, instead of being stopped by something else. Has there been a time when you started to do something to try to end your life but you stopped yourself before you actually did anything? If yes, describe:	Yes No   Total # of aborted _____	
Preparatory Acts or Behavior: Acts or preparation towards imminently making a suicide attempt. This can include anything beyond a verbalization or thought, such as assembling a specific method (e.g., buying pills, purchasing a gun) or preparing for one's death by suicide (e.g., giving things away, writing a suicide note). Have you taken any steps towards making a suicide attempt or preparing to kill yourself (such as collecting pills, getting a gun, giving valuables away or writing a suicide note)? If yes, describe:	Yes No  	
Suicidal Behavior: Suicidal behavior was present during the assessment period?	Yes No  	
Suicide:	Yes No  	
Answer for Actual Attempts Only	Most Lethal Attempt Date:	
Actual Lethality/Medical Damage: 0. No physical damage or very minor physical damage (e.g., surface scratches). 1. Minor physical damage (e.g., lethargic speech; first-degree burns; mild bleeding; sprains). 2. Moderate physical damage; medical attention needed (e.g., conscious but sleepy, somewhat responsive; second-degree burns; bleeding of major vessel). 3. Moderately severe physical damage; medical hospitalization and likely intensive care required (e.g., comatose with reflexes intact; third-degree burns less than 20% of body; extensive blood loss but can recover, major fractures). 4. Severe physical damage; medical hospitalization with intensive care required (e.g., comatose without reflexes; third-degree burns over 20% of body; extensive blood loss with unstable vital signs; major damage to a vital area). 5. Death	Enter Code _____	
Potential Lethality: Only Answer if Actual Lethality=0 Likely lethality of actual attempt if no medical damage (the following examples, while having no actual medical damage, had potential for very serious lethality: put gun in mouth and pulled the trigger but gun fails to fire so no medical damage; laying on train tracks with oncoming train but pulled away before run over). 0 = Behavior not likely to result in injury 1 = Behavior likely to result in injury but not likely to cause death 2 = Behavior likely to result in death despite available medical care	Enter Code _____	

